4.12 Removal of Patients from Protocol Therapy

Patients will be removed from protocol therapy and the PI notified when any of the criteria listed in section 4.5 apply. The reason for discontinuation of protocol therapy will be documented on the eCRF.

In case a patient decides to prematurely discontinue protocol therapy ("refuses Treatment or withdraws consent") the patient should be asked if she or he may still be contacted for further scheduled study assessments. The outcome of that discussion should be documented in both the medical records and in the eCRF. Excessive patient withdrawals from protocol therapy or from the study can render the study un-interpretable; therefore, unnecessary withdrawal of patients should be avoided.

4.13 Study Withdrawal

If a patient decides to withdraw from the study (and not just from protocol therapy) all efforts should be made to complete and report study assessments as thoroughly as possible. The investigator should contact the patient or a responsible relative by telephone or through a personal visit to establish as completely as possible the reason for the study withdrawal. A complete final evaluation at the time of the patient's study withdrawal should be made with an explanation of why the patient is withdrawing from the study. If the reason for removal of a patient from the study is an adverse event, the principal specific event will be recorded on the eCRF.

5.0 DRUG INFORMATION

5.1 Investigational Agent Description and Management

5.1.1 Description and Characteristics of Drug

Brigatinib is a novel, orally active, small molecule tyrosine kinase inhibitor (TKI). Brigatinib drug substance is isolated in crystalline form as a free base. Brigatinib has a melting point of 214°C (determined by differential scanning calorimetry [DSC]). The aqueous solubility of brigatinib is pH-dependent (e.g., at a pH of approximately 2.4, aqueous solubility is > 300 mg/mL, and at a pH of approximately 7.2, aqueous solubility is 11 mg/mL). Brigatinib does not contain any chiral centers.

5.1.2 Formulation

Brigatinib drug product is supplied as film-coated tablets, which contain brigatinib active pharmaceutical ingredient (please refer to pharmacy manual). All strengths are dose-weight proportional and manufactured with a commonblend including typical pharmaceutical excipients (lactose monohydrate,

CONFIDENTIAL

microcrystalline cellulose, sodium starch glycolate, hydrophobic colloidal silica, magnesium stearate); tablet film-coating is comprised of typical pharmaceutical grade coating components (talc, polyethylene glycol, polyvinyl alcohol, titanium dioxide).

The drug product is manufactured under Current Good Manufacturing Practice (cGMP) in accordance with approved procedures.

5.1.3 Supplier, Storage and Stability

Brigatinib will be provided at no cost to the study patient by Takeda Pharmaceuticals Inc., the manufacturer of the drug. Takeda will ship the drug to the main study center. Brigatinib will be supplied in white high density polyethylene (HDPE) bottles with induction sealed caps. Bottle labels will bear the appropriate label text as required by governing regulatory agencies. At a minimum, such text will include product name, product strength, number of tablets, lot number, and use by dating. The recommended storage condition for brigatinib is under 30°C. It should not be refrigerated or frozen.

5.1.4 Handling and Disposal

Brigatinib should be handled using standard precautions for the safe handling of antineoplastic agents. Latex gloves are recommended. It must be dispensed only from official study sites by authorized personnel according to local regulations, and stored in a secure area according to local regulations. It is the responsibility of the investigator to ensure that study drug is only dispensed to eligible study patients.

The study pharmacist or designee at the site will be responsible for handling and dispensing study drug, and completing associated documentary paperwork. The site must use an appropriate dispensing log/accountability form.

5.1.5 Return and Retention of Study Drug

All used bottles or blister packs of study drug must be returned to Takeda or destroyed in an appropriate manner according to the standard practice at each study center. Destruction of such supplies will be documented. During the study and at termination, patients must return all unused study drug supplies to their study site and the return of these unused study drug supplies must be recorded. Returned supplies must not be re-dispensed.

5.1.6 Management of Adverse Events of Note

See section 6.1.2.1 of the Investigator's Brochure for additional information on the safety of brigatinib. The study sponsor will be responsible for distributing the IB to all sites when a new version is released from Takeda.

Pulmonary Symptoms

Pulmonary events occurring within the first week of brigatinib treatment, including, but not limited to, dyspnea, hypoxia, dry cough, chest tightness, and presumptive lung infection (pneumonia) that may be accompanied by chest x-ray or CT findings of linear or ground-glass opacities should be monitored and reported. In some patients, the symptoms resolved without drug interruption, dose modification, or specific intervention. This suggests that the pathogenesis and natural history of this condition may differ from later-onset pneumonitis, rarely observed with brigatinib, but described with other TKIs. Pulmonary events have been observed after a single dose of brigatinib in patients. It is possible that patients with pre-existing pulmonary interstitial disease, including lymphangitic involvement by tumor, may be at increased risk. Nonetheless, investigators must be aware that these pneumonitis-like symptoms may present within 24 hours of initial dosing.

The management of these pulmonary events should include drug interruption, monitoring of oxygen saturation, and radiographic evaluation, and treatment with high-dose corticosteroids, supplemental oxygen therapy, and empiric antibiotics, as indicated.

The diagnosis of pneumonitis and determination of causal relationship to the drug is often confounded by the underlying disease (especially lymphangitic carcinomatosis) and other factors such as lung infection and radiation effect due to non-specific signs and symptoms as well as similar radiological appearance.

Pneumonitis should be suspected when such signs and symptoms develop or in asymptomatic patients when a new ground glass opacity or interstitial infiltration is noted in imaging studies. If a patient is considered to have the potential diagnosis of drug-related pneumonitis, physical examination, assessment of O₂ saturation, and evaluation for infectious etiologies, and thoracentesis, bronchoscopy, or open lung biopsy should be considered to reach a diagnosis

After dose interruption and symptom work-up, dose modification should be accomplished according to the recommendations in section 4.3.4 and 4.3.5 (treatment-related pneumonitis). If the symptoms include documented hypoxia and/or radiologic evidence of interstitial or ground glass changes, or result in an SAE, the early onset condition should be treated according to section 4.3.4 and 4.3.5 (treatment-related pneumonitis)

Hypertension

Brigatinib may result in elevations in BP (blood pressure, systolic or diastolic). During brigatinib treatment, BP should be regularly monitored and hypertension should be clinically managed. Brigatinib treatment might need to be temporarily interrupted if hypertension is not medically controlled.

Bradycardia

Treatment with brigatinib may result in bradycardia. An analysis of intensive ECG and PK data indicates a decrease in heart rate is associated with the timing of brigatinib maximum plasma concentrations (C_{max}). During brigatinib treatment, heart rate should be monitored at each physician visit; especially in patients who have a medical history of bradycardia.

6.0 EVALUATIONS AND ASSESSMENTS

6.1 Time and Events Table

Assessment	Screening 1	C1 D1 ^{1,2}	C1 D8 ²	C2 D1 ^{1,2,} 14	C3 D1 ^{1,2}	C4 D1 ^{1,2,} 14	C5 D1 ^{1,2}	C6 D1 ^{1,2}	C7 D1 ^{1,2}	C8 D1 ^{1,2,} 14	C9 D1 ^{1,2}	C10 D1 ^{1,2,} 14	C11 D1 ^{1,2}	C12 D1 ^{1,2}	EOT ³	FU ⁴
Informed consent ¹²	Х															
Medical History ⁵	Х														Х	
Prior cancer therapy ¹³	Х															
Physical exam & vital signs ^{5, 14}	Х	Х		Х	Х	Х	Х	Х	Х	Х	Х	Х	Х	Х	Х	
ECOG Performance Status	Х	Х		Х	Х	Х	Х	Х	Х	Х	Х	Х	Х	Х	Х	
CBC with differential ⁶	Х	Х	Х	Х	Х	Х	Х	Х	Х	Х	Х	Х	Х	Х	Х	
Serum Chemistries ⁷	Х	Х	Х	Х	Х	Х	Х	Х	Х	Х	Х	Х	Х	Х	Х	
Testosterone (males)	Х				Х		Х		Х		Х		Х			
ECG	Х															
Serum pregnancy Test ⁸	Х															
CT scan chest/abdomen ²	Х				X ²		X ²		X ²		X ²		X ²			
Brain MRI ²	Х				x ²			x ²			X ²			X ²		
Peripheral blood sample ⁹		X ⁹			X ⁹		X ⁹		X ⁹		X ⁹		X ⁹		X ⁹	
Tumor sample	x ¹⁰														X ¹⁰	
Adverse event 5, 14 assessment		Х	Х	Х	Х	Х	Х	Х	Х	Х	Х	Х	Х	Х	Х	
Patient Diary		Provide ¹¹	Review	Review	Review	Review	Review	Review	Review	Review	Review	Review	Review	Review	Review	
Concomitant Meds	Review	Review	Review	Review	Review	Review	Review	Review	Review	Review	Review	Review	Review	Review	Review	
Subsequent Therapy and Survival Status																Х
Brigatinib		See section 4.2 for brigatinib schedule and dose														

Key to Footnotes

¹ Within 28 days prior to Day 1 of brigatinib unless otherwise noted. If screening (baseline) hematology and serum chemistries were performed within 7 days of D1 of cycle 1, these do not need to be repeated.

 2 Unless otherwise noted, a window of 2 days will be applied to all study visits; for every other cycle tumor imaging starting with D1 of cycle 3, imaging may take place within 7 days prior to the study visit to accommodate holiday, weekends, and transportation issues. CT scan should be of the chest and abdomen. The pelvis should only be performed if there is evidence on metastatic disease in the pelvis.

Brain imaging MRI of the brain should be performed at baseline. In patients with known brain metastases MRI is performed every 3 cycles to assess for intracranial disease progression. Patients without brain metastases on screening MRI will undergo repeat brain imaging as clinically indicated or institutional standard (i.e. a specific interval is not mandated by the protocol). If patient cannot tolerate or has contraindication to brain MRI, a CT scan with and without contrast can be used.

³ This visit should occur 30 days (+/- 3 days) after brigatinib treatment stops for whatever reason (adverse event, progression, or at discretion of the investigator). Patients who have an ongoing grade 4 AE or SAE at the time of discontinuation from treatment will be contacted every 2 weeks until the event is resolved, determined to be irreversible by the investigator, or until the patient begins an alternate form of treatment. For patients participating on cohorts A or B who are enrolled in cohort C this visit is omitted.

⁴ Long-term follow up will occur every 3 months from the last administration of protocoldirected therapy for up to 2 years or until death, whichever occurs first. Subsequent therapy and survival status will be documented. NOTE: follow-up may occur via review of medical records, on-site visits are notrequired.

⁵ Complete history at baseline only, thereafter focused history on symptoms/adverse event. Blood pressure and heart rate should be checked at each physician visit

⁶ This includes CBC with differential and platelet count

⁷ Serum chemistries include blood urea nitrogen (BUN), creatinine, bilirubin, ALT(SGPT), AST (SGOT), alkaline phosphatase, amylase, creatinine phosphokinase (CPK). Additional can be ordered if clinically indicated or at the discretion of the investigator but are not required by the protocol

⁸ Within 7 days of D1 of treatment with brigatinib in women of child-bearing potential

⁹ This blood sample will be used to explore whether resistance mutations can be detected in ctDNA; see laboratory manual for additional details. Sample is to be drawn on C1D1 and Day 1 of every odd cycle (3, 5, etc.) while patient is receiving treatment with brigatinib.

¹⁰ Biopsy after progression on previous ALK inhibitor and within 60 days prior to D1 of treatment is mandatory (i.e., if tissue available from pre-study biopsy, this

tissue will be accessed for correlative studies, otherwise, patients must consent to tumor biopsy to meet eligibility criteria). All subjects must consent to provide tumor blocks or slides. Patients treated on cohorts A or B and enrolling in cohort C are required to undergo biopsy.

Biopsy specimens and peripheral blood samples will be destroyed as per standard institutional procedures at the time study termination or may be stored for future research. **Patients will be provided both options on the informed consent document.**

¹¹ On C1D1 provide the patient diary for use. D1 of all subsequent cycles patient diary is to be collected from previous cycle, reviewed with the patient, and a new diary provided.

¹² Patients in cohort A and B are brigatinib treatment naïve and receiving brigatinib at a standard dose. Patients in cohort C will have progressed on brigatinib and will be receiving a higher than the standard dose brigatinib. Depending on the institutional practice and policies this may require patients on cohort C to sign a "post-progression" treatment informed consent document.

¹³ Prior systemic therapy will be collected including number of prior ALK TKI's and names, prior chemotherapy treatment. The sites of disease progression (CNS, extra-CNS or both) and if the patient received local therapy (e.g. radiation therapy, SBRT, etc.) to site of disease progression between disease progression and enrollment in study (i.e. disease progression in brain and lungs, brain metastases treated with SBRT and lungs metastases or primary not)

¹⁴ Even day cycle visits not including Brain MRI imaging and are conducted (at treating physician's discretion) as telemedicine visits will not include standard clinic assessments (i.e., symptoms/adverse event, blood pressure and heart rate). To maintain data integrity, these missed assessments are to be noted in the EDC as deviations (planned) and indicate that visit was conducted remotely.

6.2 **Pre-Study Assessments**

The assessments required as part of screening can be completed in one or more visits, as long as the assessments are completed within the time frames listed in the Key to the Time and Events table.

Clinical evaluation: complete history, comprehensive physical examination (to include height and weight), vital signs, ECOG performance status

Laboratory studies:

- **Pregnancy Test**: Serum pregnancy test is required for all women of childbearing potential within 7 days prior to D1
- Hematology: CBC with differential
- Serum Chemistries: blood urea nitrogen (BUN), creatinine, bilirubin, ALT (SGPT), AST (SGOT), alkaline phosphatase, amylase, creatinine phosphokinase (CPK)
- Serum Testosterone: Limited to male patients

Cardiac studies: ECG

Tumor measurement: Tumor imaging should remain consistent throughout study, and should always include CT scans of chest and abdomen. CT scan of the pelvis should only be done if there is known metastatic disease to the pelvis. Brain MRI should be done, and if the patient cannot tolerate or has contraindication to MRI a CT scan with and without contrast should be done.

Concomitant medications: Documentation of all concomitant medications, and in particular any drugs that moderately or strongly inhibit or induce CYP3A4 and/or CYP2C8. **NOTE**: Patients will be instructed to bring their list of medications (all, including over the counter medications) to each study visit for review by their study team and for all visits to healthcare professionals (e.g., primary care physicians, consultants) while on study.

Patient diary: Patients will be provided a diary at baseline and instructed to document all doses of study medication (referenced herein as Appendix B, see as independent IRB/REB approved (patient) document).

Tissue acquisition: Tumor biopsy after progression on previous ALK inhibitor and within 60 days prior to study entry is mandatory i.e., if tissue available from pre-study biopsy, this tissue will be accessed for correlative studies, otherwise, patients must consent to tumor biopsy to meet eligibility criteria; see section 6.6 and laboratory manual for additional details. If patients have undergone NGS testing, as part of standard of care, on tumor sample after experiencing disease progression on prior therapy and prior to starting study therapy we will collect redacted report. If not performed/unavailable, sites will note not performed/not available in the database.

Prior cancer therapy: Prior systemic therapy will be collected including number of prior ALK TKI's and names, prior chemotherapy treatment. The sites of disease progression (CNS, extra-CNS or both) and if the patient received local therapy (e.g. radiation therapy, SBRT, etc.) to site of disease progression between disease progression and enrollment in study (i.e. disease progression in brain and lungs, brain metastases treated with SBRT and lungs metastases or primary not)

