Brigatinib is predicted to maintain activity against all *ALK* resistance mutations, and such resistance mutations are associated with progression in approximately 50% of patients treated with alectinib.(Gainor et al. 2016; Shaw et al. 2019; Lin, Riely, and Shaw 2017) Brigatinib inhibits ALK with approximately 2-fold greater potency than alectinib in vitro. Steady-state levels of exposure of brigatinib in patients treated with 90 mg daily for 7 days followed by 180 mg daily regimen of brigatinib are at least 2-fold higher than those achieved in patients treated with alectinib (600 mg twice daily), suggesting that brigatinib may also be less susceptible to pharmacologic resistance mutations may be unique for alectinib. Investigating brigatinib in patients who have progressed on only alectinib will create a more homogenous cohort, and there is a clinical need to assess the activity of other ALK inhibitors as alectinib is adopted as a first-line therapy.

Rationale for dose escalation cohort.

The rationale for escalation to 240 mg daily at disease progression is to attempt to overcome potential pharmacologic resistance at 180 mg daily brigatinib (i.e. to increase brigatinib exposure in order to have better activity against a given ALK resistance mutation may be dose dependent or for increased exposure in the CNS to treat CNS disease progression). A higher dose of brigatinib may have inhibitory activity against resistance mutations, and better CNS penetration which is clinically relevant since many patients experience progressive CNS disease. In the phase 1/2 dose-limiting toxicities (DLT) were grade 3 alanine aminotransferase (ALT) in one patient at 240 mg daily and grade 4 dyspnea in one patient at 300 mg daily.(Gettinger et al. 2016) The maximum tolerated dose was not established. In patients who were treated with 240 mg daily, 300 mg daily or 120 mg twice daily (n=15) the grade 3 or 4 adverse events observed at (>5%) were fatigue (13%), diarrhea (13%), headache (7%), vomiting (14%), increased lipase (13%), hypertension (7%), and pyrexia (7%). Since exposure to lower starting doses of brigatinib has now been associated with an abrogation of early onset pulmonary symptoms at escalation to a higher dose (e.g. 90 mg for 7 days before increasing to 180mg as in ALTA), re-exploration of the tolerability and efficacy of 240 mg QD after tolerable exposure to 180 mg is appropriate clinical question for further study.

Study design

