Five patients each experienced a single later-onset pneumonitis event. Four of these occurred with the most recent dose being 180 mg QD, and 1 occurred at a dose of 90 mg QD. In 3 cases, brigatinib was successfully restarted without recurrence of pneumonitis. In 1 case, the patient had already permanently discontinued due to progression of disease. In the last case, the patient permanently discontinued brigatinib due to the event

Bradycardia

Bradycardia TEAEs of any grade occurred in 5.5% (12/219) of patients overall (Arm A: 6.4% [7/109] and Arm B: 4.5% [5/110]). Sinus bradycardia and bradycardia TEAEs occurred in 3.7% (8/219) and 1.8% (4/219) of patients overall, respectively. None of the bradycardia events were Grade \geq 3. There were no dose reductions or treatment discontinuations due to bradycardia.

Hypertension

Hypertension TEAEs of any grade occurred in 22.4% (49/219) of patients overall (CSR AP26113-13-201 Table 14.3.3.4). Hypertension TEAEs were reported in a greater proportion of patients in Arm B than in Arm A (27.3% [30/110] vs 17.4% [19/109], respectively). Grade 3 hypertension TEAEs occurred in 6.8% (15/219) of patients overall; 5.5% (6/109) and 8.2% (9/110) of patients in Arm A and Arm B, respectively (CSR AP26113-13-201 Table 14.7.2.2). No Grade 4 hypertension has been reported. One patient in Arm A had retinopathy hypertensive. One patient in each arm (0.9%) had a dose reduction due to hypertension. No patient discontinued brigatinib due to hypertension.

Elevated Insulin/Hyperglycemia Events

Elevated insulin/hyperglycemia TEAEs of any grade occurred in 5.5% (6/109) in Arm A and 11.8% (13/110) in Arm B. The elevated insulin/hyperglycemia events that occurred in >2 patients in either treatment arm by PT were hyperglycemia (3.7% [4/109] of patients in Arm A and 5.5% [6/110] of patients in Arm B) and diabetes mellitus (0.9% [1/109] of patients in Arm A and 4.5% [5/110] of patients in Arm B). Elevated insulin/hyperglycemia events Grade \geq 3 occurred in only 1 patient; this patient had a Grade 3 event of diabetes mellitus (which was also present in the previous 31 May 2016 data extraction) (Study AP26113-13-201 Table 14.3.7.2.7). No patients have had dose reduction or treatment discontinuation due to increased insulin/hyperglycemia TEAEs.

Pancreatic Events

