2.2 Secondary Objectives

- **2.2.1** Further characterize treatment-related adverse events associated with brigatinib including at different doses in patients with ALK+NSCLC
- **2.2.2** Estimate duration of response in patients with ALK+ NSCLC treated with brigatinib who have progressed after prior ALK inhibition
- **2.2.3** Estimate PFS in patients with ALK+ NSCLC treated with brigatinib who have progressed after prior ALK inhibition

- **2.2.4** Estimate intracranial and extra-cranial PFS in patients with ALK+ NSCLC treated with brigatinib who have progressed after prior ALK inhibition
- **2.2.5** Estimate OS in patients with ALK+ NSCLC treated with brigatinib who have progressed after prior ALK inhibition

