8.2 Sample Size and Accrual

With the number of sites being increased, the study is expected to complete accrual (40 patients in each of the 3 cohorts) in about 2 years from amendment approval. The primary endpoint is objective tumor response of brigatinib via RECIST1.1. A true response rate of 20% would be considered active and worthy of further investigation, and a response rate of 5% will be considered inactive and not worthy of further investigation.

A two-stage design will be used for this study. (Simon 1989) Twenty patients will be initially entered in Stage I of the study for each cohort, assuming all twenty are eligible. If there are at least 2 responses among the 20 eligible patients, an additional 20 patients will be entered into that cohort. If there are fewer than 2 responses among the first twenty patients in a cohort, then the cohort will be stopped early for futility. If at least 5 responses are observed among the 40 eligible patients in a cohort, then the treatment will be considered promising for that cohort population.

Table below gives the characteristics of this design as a function of the true response rate.

If the true response rate of a cohort is 20%, for example, then the probability of stopping that cohort early for futility is 7% and the overall probability of rejecting the treatment for that cohort after the second stage is 11%. This is comparable to a power of 89%. If the true response rate of a cohort is 10%, the probability of stopping that cohort early is 39% and the overall probability of rejecting the treatment for that cohort after the second stage is 67%.

		PROBABILTY OF RESPONSE							
	0.05	0.10	0.15	0.20	0.25	0.30			
Probability of stopping early (<2 responses)	0.74	0.39	0.18	0.07	0.02	0.008			
Probability >1 responses during stage 1 (and rejecting the treatment)	0.22	0.28	0.14	0.04	0.01	0.002			
Overall probability of rejecting the treatment	0.96	0.67	0.32	0.11	0.03	0.009			

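### Lipase, a leading grade 3 or higher laboratory event in the protocol's own background data, is not in the required chemistry panel, so its rate may be under-ascertained

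*Combined protocol and SAP*

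**What the plan says.** Footnote 7 to the Time and Events Table (section 6.1) defines the required panel: "Serum chemistries include blood urea nitrogen (BUN), creatinine, bilirubin", then ALT and AST, then "alkaline phosphatase, amylase, creatinine phosphokinase (CPK"). It adds: "Additional can be ordered if clinically indicated or at the discretion of the investigator but are not required by the protocol". The same eight analytes are listed for screening (6.2), day 1 of each cycle (6.3.1), day 8 of cycle 1 (6.3.2) and end of treatment (6.4). The eligibility laboratory table (3.1.9) also has amylase. Lipase and glucose appear in none of these places, and the panel is the same for all three cohorts.

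Secondary objective 2.2.1 is: "Further characterize treatment-related adverse events associated with brigatinib including at different doses in patients with ALK+NSCLC". Section 1.1 adds that Cohort C is meant to show whether escalation to 240 mg is safe and tolerable.

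**The concern.** A rise in lipase is a laboratory finding. If the plan does not schedule the test, an asymptomatic rise enters the adverse event data only when an investigator happens to order it. The reported rate then mixes the true rate with local testing habits, and its denominator is unknown.

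Three things are at stake. One is the lipase rate reported within each cohort under objective 2.2.1. Another is what Cohort C can say about tolerability at 240 mg, where the protocol's prior evidence is 15 patients. The third is any descriptive comparison with ALTA.

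Grade-based rules also depend on the result. Cohort C entry (3.2.3) requires prior 180 mg treatment without drug-related toxicity above grade 2. The Cohort C toxicity table (4.5) acts on whether a non-hematologic event is grade 3 or 4 and whether grade 3 lasts 7 days. Whether a lipase elevation reaches those rules depends on whether anyone measured it.

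**Working it through.** **1. What is measured.** Required: BUN, creatinine, bilirubin, ALT, AST, alkaline phosphatase, amylase, CPK. Not required at any visit: lipase, glucose.

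**2. What the background reports for lipase.**
- Section 1.1, rationale for the dose escalation cohort: 13% grade 3 or 4 among 15 patients pooled over 240 mg daily, 300 mg daily and 120 mg twice daily. 2/15 = 13.3%, so the figure is consistent with two patients; exact 95% CI 1.7 to 40.5%. Seven grade 3 or 4 events are listed there by rate: fatigue, diarrhea, headache, vomiting, lipase, hypertension and pyrexia. Lipase is the only one of the seven that needs a blood test.
- Section 1.3.9, ALTA safety: joint most common treatment-related grade 3 or higher event in Arm A, with hypertension, 4/109 = 3.7%. Dose interruption in 7/219 = 3.2%. Dose reduction in 1/109 and 2/110, three patients in all.

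**3. Would symptoms trigger the test?** ALTA pancreatic enzyme elevations of any grade: 45/219 = 20.55%, printed as 20.5% (exact 95% CI 15.4 to 26.5%). By arm: 18/109 = 16.5% and 27/110 = 24.5% (Fisher p = 0.18). Clinical pancreatitis: none. Symptoms are therefore not a dependable prompt.

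**4. Is there a dose trend in ALTA?** Grade 3 or higher lipase: 5/109 = 4.6% (Arm A) and 4/110 = 3.6% (Arm B). There is no rise with dose.

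**5. Glucose.** Section 1.3.9 states: "Elevated insulin/hyperglycemia TEAEs of any grade occurred in 5.5% (6/109) in Arm A and 11.8% (13/110) in Arm B". The Fisher p-value is 0.15. This is a composite. The term hyperglycemia alone is 4/109 = 3.7% and 6/110 = 5.5% (Fisher p = 0.75); diabetes mellitus is 1/109 and 5/110. One patient had a grade 3 or higher event, and there were no dose reductions or discontinuations.

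**6. Size of a possible shortfall.** Section 8.2 plans "40 patients in each of the 3 cohorts". Expected detected events = 40 × rate × f, where f is the share of events caught by discretionary testing. No document gives f, so the values below are assumptions.

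| f | Grade 3–4 lipase, rate 2/15 | Grade ≥3 lipase, rate 4/110 |
|---|---|---|
| 1 | 5.3 | 1.5 |
| 0.75 | 4.0 | 1.1 |
| 0.5 | 2.7 | 0.7 |
| 0.25 | 1.3 | 0.4 |

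The rate is itself very uncertain. At the limits of the interval for 2/15, the fully ascertained count in 40 runs from 40 × 0.017 = 0.7 to 40 × 0.405 = 16.2. The table shows the direction of the effect; it does not estimate the shortfall.

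**The case against.** The case on the other side is substantial.

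- **Amylase is required at every chemistry draw**, and section 1.3.9 groups amylase and lipase as pancreatic enzyme elevations. Pancreatic monitoring is thus partly systematic. This stands and limits the point, but amylase does not supply a lipase grade.
- **Extra tests are allowed, and abnormal laboratory findings count as adverse events** (7.2.1). This also stands: some lipase events will be captured. It does not give a known denominator.
- **No comparison across cohorts is planned.** Section 8.3 analyzes the cohorts separately. The same panel applies to all of them, so the omission alone does not distort a dose contrast; discretionary testing would also have to differ by cohort, and nothing in the documents shows that it does. This stands. The rate within each cohort and any descriptive reading against ALTA remain affected.
- **The 13% may not carry over to Cohort C.** It pools three regimens, and Cohort C patients are selected for having tolerated 180 mg. This stands.
- **Section 5.1.6 names pulmonary events, hypertension and bradycardia**, not pancreatic events, as those needing management guidance. True, but objective 2.2.1 is wider than that list.

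A reader might infer that hyperglycemia is a main event that doubles between 90 and 180 mg. The documents do not support this: the doubling belongs to the composite, the difference is compatible with chance, and Arm B also started at 90 mg.

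**Conclusion.** The required panel leaves out lipase at every visit and in every cohort, although the protocol's own data make it a leading grade 3 or higher laboratory event. Lipase events may be under-ascertained. That weakens objective 2.2.1, the Cohort C tolerability assessment and descriptive comparison with ALTA. The glucose gap is real but secondary.

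A reader might go further and conclude that lipase will be under-counted by a stated fraction, or that the 240 mg against 180 mg contrast will be biased. Neither is supported. The extent depends on a testing share the documents do not give and on a rate whose interval is 1.7 to 40.5%, and a biased contrast needs unequal testing between cohorts.

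The conclusion rests on two premises: most lipase elevations are asymptomatic, as the ALTA pancreatic data suggest, and discretionary testing will not be universal. The primary ORR analysis, sample size and error rates are unaffected. This is a minor point with a cheap remedy.

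**What to change.** Reconcile the panel in footnote 7 and sections 6.2, 6.3.1, 6.3.2 and 6.4 with objective 2.2.1 and with the grade-based passages in 3.2.3 and 4.5. No change to those clinical rules is proposed here. Either of two routes would do:

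1. **Record lipase, and secondarily glucose, systematically** at the visits where chemistry is already drawn. The cost is the added assays and more asymptomatic elevations to record and grade.
2. **Leave the panel alone and limit the claim in 8.3.** State that lipase and glucose event rates rest on discretionary testing, report the number of patients tested in each cohort as the denominator, and do not compare these rates across cohorts or with ALTA. The cost is a short addition to 8.3 and a count of patients tested. A rate among those tested describes only them, and may run high if testing follows suspicion, so the text should say so.

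The first route lets the trial estimate the rate; the second only makes the limitation explicit.
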